Hypothesis 4. Progression of disease: Markers of disease progression are lacking in ATTR CA. We hypothesize that attainment of a hierarchical composite endpoint at 1-year of death, heart failure hospitalization, and 30% decline in 6-minute hall walk will be higher in ATTRm vs. ATTRwt CA. In addition, we will explore the capacity of specific markers to assess disease progression including: (1) established circulating biomarkers such as troponin I/T, NT-proBNP, BNP and Galectin-3, (2) novel biomarkers such as RBP4 and TTR concentration, (3) ECG, and

echocardiographic measures including longitudinal strain and MCF, (4) functional capacity by 6-minute hall walk and SPPB, and (5) QOL. Our preliminary data and published work⁹ suggests reduced median survival for ATTRm Val122Ile CA (25 months) vs ATTRwt (43 months) in different race cohorts. We hypothesize that we will observe reduced survival and greater functional decline in ATTR Val122Ile vs ATTRwt within race cohorts.

Hypothesis 5. Performance of risk calculator: Our point-of-care risk calculation utilizing RBP4 and TTR concentration with echocardiographic and ECG determined parameters will be tested in this cohort. We will re-derive the prediction model based upon clinical variables noted above. We anticipate showing a similar degree of accuracy (ROC AUC > 0.95) for identification of cases with ATTR vs. controls

Specific Aim 2: To demonstrate that circulating RBP4 concentration is integral to TTR tetramer stability, which in turn determines the clinical characteristics of ATTR CA. We will measure TTR tetramer stability and RBP4 concentration in serum and urine collected in Aim 1. The overall hypotheses of this Aim are that measurements of TTR kinetic stability, RBP4 and TTR concentration will differentiate patients with ATTR CA vs. non-amyloid HF controls and associate with disease progression and outcomes. Specific hypotheses are as follows:

Hypothesis 1: TTR kinetic stability and RBP4 concentration: We hypothesize that at baseline, TTR kinetic stability will be lower in ATTR CA vs. non-amyloid HFpEF, and that stability will be inversely proportional to plasma RBP4 concentration. We further hypothesize that TTR kinetic stability will be lower for ATTRm vs. ATTRwt.

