2.1.8 Data Analysis Plan

Descriptive statistics will be used to summarize subjects' demographics and study outcomes. Sample proportions with exact 95% confidence intervals will be used to estimate the overall prevalence of ATTRm CA in Blacks and Hispanics and by sex. All analyses will be performed in SAS v.9.4 (Cary,NC), at a significance level of 0.05.

AIM 1: Hypotheses 1-3: The differences in proportions for prevalence (#1), genetic mutation status (#2), and sex (#3) will be assessed using Chi-squared/Fisher Exact tests. The genetic ancestry analysis will use 500K SNP data to perform principal components analysis (PCA) and determine the percentage of African admixture in all participants. To identify the associations of rare genetic variants in the TTR gene in ATTR CA cases vs controls, we will utilize burden testing.⁹⁴ **Hypothesis 4:** The main analysis will use the Kaplan-Meier method to estimate the probabilities of the composite endpoint, with medians (95% CI) being reported for each group. Cox regression analysis will be performed to generate the hazard ratio (95% CI), and to allow adjustment for other covariates such as sex or race/ethnicity, or explore interaction with other variables including cardiac biomarkers, echo parameters, or QOL. Alternatively, we will apply and compare Finkelstein-Schoenfeld's unmatched approach⁹⁵ to the matched win ratio,⁹⁶ both methods being used for reporting composite endpoints, with more appropriate priority given to the more clinically important event, e.g. mortality. **Hypothesis 5:** We will test the clinic-based risk calculator that was previously developed and validated in a smaller matched cohort study.⁹⁷ The proposed 4-variable model included: RBP4, LVEF, inter-ventricular septal thickness, mean limb lead QRS voltage, and generated an ROC AUC >90%. This model will be tested in our larger cohort and assessed with respect to prediction capability (AUC ROC) and goodness-of fit (Hosmer-Lemeshow test). We also plan to fit additional multivariable logistic regressions using the variables collected employing variable selection/model-building strategies and comparing the

resulting model(s) to the one proposed above. The variables in the final clinical risk model will be based on weights from the multivariate model.

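### Hypothesis 5 compares a calculator selected and fitted on the SCAN-MP patients with a fixed 4-variable model on the same patients, without optimism correction, so a real gain cannot be told from overfitting

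*Combined protocol and SAP*

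**What the plan says.** In Section 2.1.8 (Data Analysis Plan, Aim 1, Hypothesis 5) the existing calculator is described as "previously developed and validated in a smaller matched cohort study". Its content is given: "The proposed 4-variable model included: RBP4, LVEF, inter-ventricular septal thickness, mean limb lead QRS voltage". Its reported performance is that it "generated an ROC AUC >90"%. For this study, "This model will be tested in our larger cohort and assessed with respect to prediction capability (AUC ROC) and goodness-of fit (Hosmer-Lemeshow test").

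The same section then plans additional multivariable logistic regressions on the variables collected, "employing variable selection/model-building strategies and comparing the" "resulting model(s) to the one proposed above". It closes by saying that the final clinical risk model will rest on weights from the multivariable fit.

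Section 2.1.6 (Hypothesis 5) adds: "We will re-derive the prediction model based upon clinical variables noted above". It expects a "similar degree of accuracy (ROC AUC > 0.95").

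The plan does not give a candidate list, a selection procedure, the measure on which the models are compared, or a criterion for choosing between them. It does not mention a split sample, cross-validation, bootstrap, shrinkage or a separate validation set for the new model. The synopsis names only the domains: clinical, electrocardiographic, echocardiographic and biochemical.

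**The concern.** The two AUCs are not the same kind of quantity. For the existing calculator, the SCAN-MP patients are new data, so its AUC is an external validation. For the refit, the same patients choose the variables, set the coefficients and then supply the score. That is an apparent AUC, and it is optimistic. The Hosmer-Lemeshow test does not fill the gap, because a model fitted to these patients tends to look calibrated in them.

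Two outputs are affected. One is the comparison of the new calculator with the old. The other is any statement that the new calculator meets the expected AUC above 0.95.

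**Working it through.** The plan gives no power, precision or sample-size figure for Hypothesis 5, so there is nothing of its own to reproduce. The check is by simulation.

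**Inputs from the document**
- 800 patients with 80-160 cases (Section 2.1.7). The hypothesised 10-15% prevalence gives 0.10 × 800 = 80 to 0.15 × 800 = 120; the figure of 160 needs 20%.
- A fixed model with 4 predictors, source AUC above 0.90, expected AUC above 0.95.

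**Assumptions, not in the document**
- 15 or 30 candidate variables in total (20 in the bootstrap runs), of which 4 are true predictors and the rest noise. The case report forms would allow more: about 43 echocardiographic fields, 28 numbered history items and about nine quantitative ECG fields.
- Backward elimination at p<0.05 or p<0.157; independent normal predictors.
- Fixed weights either ideal or with 30% random error.

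**Formulas**
- Total separation d = √2 × z(AUC): √2 × 1.2816 = 1.812 for AUC 0.90, and √2 × 1.6449 = 2.326 for AUC 0.95. Each of the four predictors is shifted by d/2 in cases.
- Optimism = apparent AUC − true AUC, the true value being computed exactly from the fitted coefficients.

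**Ideal fixed weights, selected settings (200-300 replicates each)**

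| True AUC of fixed model | Cases | Candidates | Threshold | Apparent, fixed | Apparent, refit | True, refit | Optimism | Refit looks better |
|---|---|---|---|---|---|---|---|---|
| 0.90 | 160 | 15 | 0.05 | 0.899 | 0.902 | 0.897 | 0.005 | 93.7% |
| 0.90 | 120 | 30 | 0.157 | 0.900 | 0.911 | 0.889 | 0.022 | 100% |
| 0.90 | 80 | 30 | 0.05 | 0.899 | 0.908 | 0.892 | 0.016 | 97.7% |
| 0.95 | 160 | 15 | 0.05 | 0.951 | 0.953 | 0.948 | 0.005 | 97.5% |
| 0.95 | 80 | 30 | 0.05 | 0.949 | 0.954 | 0.945 | 0.009 | 98.0% |
| 0.95 | 120 | 30 | 0.157 | 0.950 | 0.957 | 0.943 | 0.014 | 100% |

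At true AUC 0.90, over all case counts, candidate numbers and thresholds, the refit was truly worse in every run. It nevertheless had the higher apparent AUC in 92-100% of runs (87.5% in one 40-replicate run). The largest optimism came with 80 cases, 30 candidates and p<0.157: 0.915 − 0.886 = 0.029. The true loss ran from 0.0028 to 0.900 − 0.886 = 0.014. In all three settings at 0.95, the refit's mean apparent AUC is above 0.95 while its mean true AUC is below it.

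A separate simulation with about 88 cases, 24 or 44 candidates and true AUC 0.86 or 0.92 (150 datasets per setting) gave optimism of 0.011-0.025. The refit looked better in 96.7-98.7% of datasets, with a true loss of 0.005-0.012.

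**Fixed weights 30% off, AUC 0.90 before the error (six settings, 80 or 120 cases).** The refit was truly worse in 26-78% of runs, and in those runs it looked better 97-100% of the time. The mean apparent gain was 0.0108 to 0.0216 against a mean true gain of −0.0066 to +0.0044. The gain was overstated in every setting, by between 0.0108 − 0.0044 = 0.0064 and 0.0216 + 0.0066 = 0.0282.

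**A significance test does not cure it.** With ideal fixed weights, a two-sided 0.05 DeLong test on the same patients wrongly favoured the refit in 7-49% of runs, against a nominal 2.5% in that direction.

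**The correction does.** Bootstrap with the selection repeated (20 candidates, p<0.05, AUC 0.90, 40 replicates of 30 resamples):
- 80 cases: apparent 0.901, corrected 0.883, true 0.894. The refit looked better in 87.5% of runs before correction and 0% after.
- 120 cases: apparent 0.909, corrected 0.895, true 0.895. The refit looked better in 97.5% before and 5% after.

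These few replicates are approximate, and the correction leans cautious. It subtracts 0.018 and 0.014. The fixed model itself scored 0.896 and 0.904 in these samples instead of 0.900; allowing for that, the optimism is about 0.901 − 0.894 + 0.004 = 0.011 and 0.909 − 0.895 − 0.004 = 0.010.

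**The case against.** **No choice rule is stated.** A reader might infer that the plan selects whichever model has the higher apparent AUC, and so picks the overfitted one nearly every time. The document does not support that. It says the models will be compared, without naming a measure or a criterion, and the closing sentence says where the final weights come from, not that they belong to the winner of an AUC contest. The absence of optimism correction is itself an inference from silence. This stands, and limits the point to a biased comparison.

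**The refit may be the better model.** A reader might also infer from the 88-100% figure that the wrong model is being favoured. That follows only when the fixed weights are near ideal and every other candidate is noise. The existing model comes from a smaller matched cohort, and Section 1.4.4 reports an AUC of 0.773 for myocardial contraction fraction, which is not among the four variables. In runs with 88 cases, 20 noise variables, fixed AUC 0.90 and elimination at 0.05 (200 replicates), the refit was truly better in:
- 0% with ideal weights and no other signal;
- 59% with weights 30% off;
- 73.5% with three extra predictors of AUC 0.60;
- 92% with both (mean true gain +0.010);
- 90.5% with one extra independent predictor of AUC 0.678.

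This stands too. It does not rescue the comparison, because the apparent AUC favours the refit in either situation and so cannot separate them.

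**The effect is small and the analysis is not central.** A true loss of 0.005-0.012 is below the sampling SD of the fixed model's own AUC, about 0.018 in those runs. The synopsis lists the calculator among items to explore, although Sections 2.1.1 and 2.1.6 make it a hypothesis, and no prevalence or outcome analysis depends on it. That limits the priority. But optimism runs in one direction, unlike sampling error, and a confidence interval around an uncorrected AUC does not reveal it.

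**Conclusion.** The concern holds as a defect of the comparison. A model selected and fitted on the SCAN-MP patients is set against a fixed external model on the same patients, with no provision for optimism. The refit's apparent AUC is biased upward relative to the fixed model by about 0.005-0.03, given 80-160 cases, 15-44 candidates and backward elimination. More candidates, looser selection and fewer cases push it up.

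With a near-ideal fixed model and noise candidates, the refit looks better in about 88-100% of datasets while truly about 0.003-0.014 worse. Otherwise it may truly be better, but its AUC and its gain are still overstated, and an AUC just above 0.95 could be reported for a model that does not reach it. If the four variables' weights were also re-estimated here, both models would carry optimism and the gap would narrow, with the selected model still carrying more.

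The direction is secure; the size rests on the assumptions above. It should be changed, but it does not threaten the study's main results.

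**What to change.** In Section 2.1.8, Hypothesis 5:

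1. State that the 4-variable model is applied with its coefficients from the source cohort, and print them; the document does not give them.
2. List the candidate variables and the selection procedure before the outcome data are analysed.
3. For every refitted model, report bootstrap optimism-corrected or repeated cross-validated AUC and calibration, repeating the whole variable selection in each resample.
4. Base the comparison with the 4-variable model, and any statement about AUC above 0.95, on the corrected figures with a confidence interval.

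I would not require the interval for the gain to lie above zero before the refit is preferred. Where the fixed weights are off or new variables carry signal, that would often keep the poorer model.

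No new patients or measurements are needed. The cost is a few sentences in the plan, some computing time and a slightly lower reported AUC for the refit.

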1.2 ATTR-CM Population Burden

1.2.1 ATTR amyloid is an under-recognized cause of heart failure

Cardiac involvement in ATTR, also known as familial amyloid cardiomyopathy (FAC) when associated with variant and WT TTR aggregation, previously senile systemic amyloidosis (SSA) when associated solely with WT TTR aggregation, is caused by amyloid fibril infiltration of the myocardium. This results in diastolic dysfunction progressing to restrictive cardiomyopathy and HF. ATTR cardiomyopathy is a late onset disease with symptoms typically occurring in patients over 60 years old. Although there are more than 20 mutations which have been associated with specific cardiac involvement, one mutation, Val122Ile, has been reported with high frequency in Blacks (prevalence of 3.4% to 3.9%^{5, 45, 46}). The prevalence of ATTR dominated by a cardiomyopathy phenotype is unknown, but is certainly under-diagnosed⁴³. Both Black Val122Ile carriers and Black patients with ATTRwt, who present typically after age 60, are often mistakenly thought to have hypertensive heart disease⁴³. The prevalence of the Val122Ile allele in older adults with manifest cardiovascular disease, such as HF, is much higher. Among 207 of 650 Blacks enrolled in the BEST Trial with NYHA Class III (92%) and IV (8%) HF, with a left ventricular ejection fraction <35%, the Val122Ile variant was found in 13 (6.3 %) of the subjects⁴⁷. Of note, four of the 116 individuals in the under 60 years of age cohort (3.5%) were positive, whereas 9 of the 91 over 60 years of age (10%) had the amyloidogenic Val122Ile allele. Studies indicate that the Val122Ile mutation is 5 times more prevalent in Blacks with HF than in a community cohort of comparable age⁴⁷. Notably, a mutation in TTR is not a prerequisite for developing ATTR cardiomyopathy. In the elderly, WT (normal) TTR may become structurally unstable for unknown reasons (this will be quantitatively explored herein), resulting in deposition of amyloid fibrils primarily in heart tissue and leading to HFpEF⁴⁸⁻⁵¹. The frequency of TTR amyloid deposition in cardiac ventricles reported from autopsy studies, range from 1.8% to 25%^{52, 53}, with a rate of clinical cardiac disease pre-mortem of 34%⁵². More recent data demonstrates that among HFpEF subjects who were an average age of 74±14 at diagnosis, 21.2% had amyloid deposits on autopsy performed at an average age of 76±14 years. Of HFpEF patients ≥ age 75 years at HF diagnosis (n = 63), 20 (32%) had amyloid deposition vs. 4 of 50 (8%) patients < 75 years at HF diagnosis (p = 0.002). Of the 29 patients with amyloid deposition at autopsy, only 6 had a pre-morbid diagnosis of amyloid

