2.1.6 Hypotheses

Aim 1: To determine the prevalence of ATTR CA in Caribbean Hispanics and Blacks with HF

Hypothesis 1. Overall prevalence of ATTR CA: The prevalence of ATTR CA will be defined by the number of cases with both ATTRwt and ATTRm CA as a percentage of total enrollment. The background prevalence of Val122Ile in the US Black population is 3.4%, and we hypothesize a prevalence rate of 8% of ATTRm Val122Ile in our outpatient HF population. Since there are no data in Hispanics regarding ATTR CA prevalence, we further hypothesize that we will observe a prevalence of ATTRwt CA of 2-8% of the Hispanic population. Thus, we have conservatively defined the predicted prevalence of ATTR CA as 10-15%.

Hypothesis 2. Relative proportion of ATTR CA comprised by ATTRwt and ATTRm: As noted above, based upon the background allele frequency, we anticipate that Black patients will be much more likely to manifest ATTRm (Val122Ile) vs. ATTRwt CA, whereas Hispanic patients will be more likely to manifest ATTRwt CA. We will be able to explore the Val122Ile genotype frequency in the Hispanic population, and with the addition of cardiac amyloid scintigraphy scanning, the relative contribution of ATTRm in this population, which we postulate to be lower than Blacks. We will utilize genetic ancestry analysis data to further characterize race and ethnicity, and, as an exploratory analysis, evaluate the interaction of genetic variants identified with Val122Ile and ATTR CA as defined by radiotracer uptake.

Hypothesis 3. Proportion of gender: Published reports of ATTR Val122Ile are 75% male and reports of ATTRwt are 95% male. We hypothesize that highly sensitive cardiac amyloid scintigraphy testing will reveal a gender distribution of ATTR that is closer to 50%, based upon allele distribution. We will explore comorbidities, TTR stability, and RBP4 differences among men and women with ATTR to determine interactions with phenotypic expression.

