AIM 2: Hypothesis 1 and 3: Means (95% CI) and/or medians (inter-quartile range) will be computed for all continuous measurements including RBP4/TTR concentrations. Pearson/Spearman correlation coefficients will be calculated to quantify the strength of the association between RBP4 plasma and urine concentrations in the overall ATTR CA cohort and separately by ATTRm vs. ATTRwt groups. Linear regression models will be used to assess differences in TTR kinetic stability between the two groups, adjusting for RBP4 concentration and vitamin A. **Hypothesis 2:** In addition to descriptive statistics, linear regression models will be employed to test the associations between RBP4 concentration, TTR stability, and cardiac amyloid scintigraphy heart to contralateral chest ratio between the two groups, ATTR CA vs non-amyloid HF controls, adjusting for clinical characteristics and retinol concentration.

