
serum vitamin A, and urinary creatinine, as a means to correct for confounding factors. *Unequal percentage of subjects with insulin resistance between groups*: As serum RBP4 concentration is increased in insulin resistance, to control for the potential confounder of unequal distribution of insulin resistance across our subject groups, we will adjust the analysis by history of diabetes and serum glucose. Our preliminary data has shown that glycated hemoglobin or lipids levels do not significantly interact with RBP4 concentrations in the target HFP EF population .

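### No Aim 2 model names age or sex as a covariate, so the between-group differences in TTR stability and RBP4 are open to confounding of uncertain direction

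*Combined protocol and SAP*

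**What the plan says.** Section 2.1.8, Aim 2, gives one regression sentence for Hypotheses 1 and 3: "Linear regression models will be used to assess differences in TTR kinetic stability between the two groups, adjusting for RBP4 concentration and vitamin A". No regression is written there for the plasma or urine RBP4 contrast. Section 2.2 supplies the RBP4 corrections: "serum vitamin A, and urinary creatinine, as a means to correct for confounding factors", and, for insulin resistance, "we will adjust the analysis by history of diabetes and serum glucose". The Hypothesis 2 model compares ATTR CA with non-amyloid controls "adjusting for clinical characteristics and retinol concentration", without listing the clinical variables.

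Age and sex appear in none of these, and no matching or stratified analysis is planned for Aim 2. Elsewhere the protocol does use them. The Aim 1 Hypothesis 4 Cox model is included "to allow adjustment for other covariates such as sex or race/ethnicity", and the background survival models in 1.4.3 all adjust for age and male sex.

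The protocol also describes who the cases are likely to be. Section 1.2.1 reports, for HFpEF patients aged 75 or over against younger ones at autopsy, that "20 (32%) had amyloid deposition vs. 4 of 50 (8%) patients" under 75. Section 2.1.6 states: "Published reports of ATTR Val122Ile are 75% male and reports of ATTRwt are 95% male". Table 3 plans 400 men and 400 women, with half of the cohort over 75.

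**The concern.** Aim 2 is observational. Its groups are formed by scan result and genotype, so a variable that differs between groups and also moves the marker will bias the contrast. Age and sex are the obvious candidates. Section 1.2.1 says of age: "In the elderly, WT (normal) TTR may become structurally unstable for unknown reasons". Section 2.1.6 plans to look at stability and RBP4 differences between men and women, though only among cases.

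The wording of the Hypotheses 1 and 3 sentence adds to the problem. It follows a sentence about ATTRm and ATTRwt, so its two groups could be those genotypes or could be cases and controls. Hypothesis 1 in 2.1.6 makes a claim about both contrasts. At stake is whether a difference in stability or RBP4 can be attributed to amyloid or genotype, which is what Aim 2 sets out to show.

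**Working it through.** **1. Stated power (2.1.7).** Inputs: RBP4 difference 5, SDs 9 and 20, 80 cases v 720 controls; two-sided 0.05 is assumed because Aim 2 does not state sidedness.
- SE = sqrt(81/80 + 400/720) = 1.252. Power = Φ(5/1.252 − 1.96) = 97.9%. With 120 v 680, SE = 1.124 and power is 99.4%.
- Stability: difference 0.01, SD 0.002. Power exceeds 99.9%. The difference detectable with 80% power is 2.80 × 0.002 × sqrt(1/80 + 1/720) = 0.00066.

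Both agree with the stated >95%.

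**2. Age gap, cases v controls.** Two sources in the protocol disagree.
- Autopsy series (1.2.1): 32% v 8% is a 4:1 ratio. With 80 cases in a 400/400 age split, 64 cases (80%) and 336/720 controls (47%) are over 75.
- Table 1 ages: Val122Ile 69.5 (SD 7.9), ATTRwt 77.2 (SD 5.8). Assuming normal ages, 24% and 65% are over 75. The 2.1.7 rates give 0.08 × 600 + 0.04 × 200 = 56 ATTRm cases, leaving 24 ATTRwt of 80. Cases over 75: (56 × 0.243 + 24 × 0.648)/80 = 36%; controls: (400 − 29.2)/720 = 52%. With the 40/40 split that 2.1.7 uses for Hypothesis 4, the figures are 45% v 51%.

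**3. Sex gap, cases v controls.** With 80 cases in a 400/400 cohort: 75% male cases v 340/720 = 47% of controls; 95% v 324/720 = 45%; no gap if cases are 50% male.

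**4. ATTRm v ATTRwt.** Age 69.5 v 77.2 years (p<0.001, Table 1). Male: 75% v 95% in published reports; 83.8% v 94.7% in Table 1 (p=0.124).

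**5. False-positive rate with no amyloid effect (80 v 720).** In SD units, SE = sqrt(1/80 + 1/720) = 0.118. Bias = shift × gap, and the rejection rate is Φ(bias/SE − 1.96) + Φ(−bias/SE − 1.96). The shifts are assumed. When both factors act, they act in the same direction.

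| Scenario | 0.1 SD | 0.25 SD | 0.5 SD |
|---|---|---|---|
| 80% over 75, 75% male | 8% | 25% | 74% |
| 80% over 75, 95% male | 11% | 42% | 94% |
| 80% over 75, 50% male (age alone) | 6% | 11% | 29% |
| 36% over 75, 50% male (age alone) | 5% | 6% | 10% |

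Simulation at 0.25 SD (3,000 runs) gave 25% and 41% for the first two rows. With age and sex in the model these fell to 4.9% and 4.7%.

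**6. Bias against the planned differences.** For stability, the first row at 0.5 SD gives a bias of 0.5 × (0.333 + 0.278) = 0.306 SD, or 0.306 × 0.002 = 0.0006. That is 6% of 0.01, though close to the 0.00066 detectable with 80% power. For RBP4, sex alone would need an effect of 5/0.50 = 10 to 5/0.28 = 18 units to produce the whole planned difference of 5.

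**7. Price of adjustment.** Variance inflation = 1 + q(1 − q)D², where q is the share in one group and D² sums the squared standardised gaps in age and sex, taken as independent within groups.
- Cases v controls (80 or 120 cases, 80% over 75, 75–95% male): 1.07 to 1.24, so the SE rises by 3% to 11%. RBP4 power is 96% to 99%.
- ATTRm v ATTRwt at 40 v 40, with Table 1 ages: (7.7/6.93)² = 1.23. Sex 75% v 95%: 0.20²/0.1175 = 0.34. Inflation = 1 + 0.25 × 1.57 = 1.39, so the SE rises by about 18%.

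**The case against.** The strongest reply is that the quoted sentence may be the ATTRm v ATTRwt model. The only Aim 2 regression that explicitly names cases and controls would then be the Hypothesis 2 model, whose open covariate term can hold age and sex. The ambiguity is real, but it does not remove the gap. The genotype groups differ by 7.7 years in Table 1 and by 20 points in published sex mix, and an unlisted covariate set does not commit the analyst to either variable.

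A reader might infer that cases will be older and mostly male, so that Hypothesis 1 could be confirmed by age alone. The documents do not support that. The 80% v 47% split comes from an autopsy series of any amyloid deposition, whereas Table 1 ages with the planned rates make cases somewhat younger than controls; age would then work against Hypothesis 1 if older people are less stable. Table 1 is itself a single-institution series, so neither direction is settled. The male excess comes from earlier reports, and 2.1.6 expects a mix closer to 50% here. That expectation is under test, so it cannot justify leaving sex out.

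It is also fair that the remark on unstable wild-type TTR in the elderly describes how the disease arises, not an age effect in amyloid-free patients, and that every shift in the table is assumed. Finally, the calculation leaves out the RBP4, vitamin A and other corrections the plan does name; these could absorb part of an age or sex effect.

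**Conclusion.** The point stands as an avoidable gap in a stated model. Age and sex are absent from every Aim 2 analysis, the groups are not randomised, and the protocol's own figures make imbalance plausible on either reading of the sentence. The direction is unknown, so confounding could inflate, mask or create a small difference. The 8% to 74% range is conditional on the autopsy age gap, 75% male cases and assumed shifts of 0.1 to 0.5 SD each. Under the Table 1 ages with equal sexes it is about 5% to 10%. It is not a forecast for this cohort. For stability, confounding could not plausibly imitate the planned difference of 0.01, which is 5 SD. The exposure lies in smaller differences, which this sample size can declare significant. The change is worth making because it costs little and removes the question.

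**What to change.** In 2.1.8:
- State which groups each Hypothesis 1 and 3 model compares.
- Write a model for plasma RBP4 and one for urine RBP4.
- Include age (continuous) and sex in every Aim 2 between-group model, for ATTR CA v controls and for ATTRm v ATTRwt.
- List the clinical covariates of the Hypothesis 2 model, with age and sex among them.
- Make the adjusted difference the reported result.

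The cost is analysis-plan wording only, since date of birth and sex are on the demographics form for every participant. In the case-control contrast the variance of the group term rises by about 7% to 24%, and RBP4 power stays above the stated >95%. The price is higher for ATTRm v ATTRwt (SE up by about 18% under the inputs shown), because those groups differ more in age. That loss reflects how far age and genotype overlap in these patients.
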